3.2 Number of Study Centers

This is a multicenter, multinational study.

3.3 Number of Patients

Approximately 100 patients will be randomized in this study, with approximately 25 patients assigned to each of the 4 treatment cohorts.

3.4 Overall Study Duration and Follow-up

The length of patients' participation in the study may be up to approximately 16 months (69 weeks), which includes a 4-week screening period that includes a 2-week diet stabilization/run-in period for patients not already on a stable diet, and a 2-week qualification period, an up to 52-week treatment period, and a 13-week post-treatment follow-up period. The treatment portion of the study will be complete when the last patient reaches 6 months of exposure.

Patients may be required to attend additional visits for monitoring of AEs or abnormal investigation results. The frequency of additional monitoring will be determined by the Study Medical Monitor in consultation with the Investigator.

3.4.1 Screening

Patient eligibility for the study will be determined within 4 weeks prior to study.

3.4.2 *Treatment*

For each patient, minimum treatment duration is 6 months and a maximum of 52 weeks.

All patients enrolled will be randomized to a minimum of 6 months of treatment in 1 of 4 treatment cohorts. On completion of the 6 months, patients will continue treatment within the same randomized cohort until the last patient reaches 6 months of exposure (for continuing safety assessments), with a maximal exposure period of 12 months. The End of Treatment visits for all patients on treatment will be scheduled no later than the End of Treatment visit of the last patient to complete 6 months of exposure.

The End of Treatment visit should be scheduled one dosing interval post last dose of study drug: one week post last dose for weekly dosing (Cohort D), 2 weeks post last dose for every 2-week dosing (Cohort C), and 4 weeks post last dose for every 4-week dosing (Cohorts A-B). The procedures scheduled for the Week 53/ET visit ([Appendix A](#)) will be performed at the End of Treatment visit. Following the End of Treatment visit patients will then enter a 13-week post-treatment follow-up period.

Eligible patients will report to the Study Center for assessments at specified intervals throughout the 52-week treatment period as detailed in the Schedule of Procedures in [Appendix A](#). During the Treatment, Study Drug (ISIS 678354 or placebo) will be administered by SC injection once-weekly, every 2 weeks, or every 4 weeks, depending on cohort assignment.

3.4.3 *Post-Treatment*

Patients, when completed dosing, will enter the 13-week post-treatment follow-up period and will return to the Study Center for 3 follow-up visits at 4, 8, and 13 weeks post End of Treatment period as per [Appendix A](#) (Follow-up).

The final study visit for each patient will be 13 weeks post End of Treatment period. End of Treatment period is defined as one dosing interval post last dose.

3.5 *End-of-Study*

The End-of-Study is defined as last patient, last visit.

For individual patients, End-of-Study is defined as completion of their last study visit.

3.6 *Data and Safety Monitoring Board*

An independent Data and Safety Monitoring Board (DSMB) will be assembled to review safety, tolerability and efficacy (as needed) data collected on ISIS 678354 during this study. Based on its ongoing assessment of the safety and tolerability of ISIS 678354, the DSMB will provide recommendations to the Sponsor for modifying, stopping or continuing the study as planned. Details on the safety assessments, frequency of review, meeting schedules and controlled access to unblinded data are outlined in the DSMB Charter and/or Statistical Analysis Plan (SAP).

4. PATIENT ENROLLMENT

4.1 Screening

Before patients may be enrolled into the study, the Sponsor or designee requires a copy of the Study Center's written independent ethics committee/institutional review board (IEC/IRB) approval of the protocol, informed consent form, and all other patient directed information and/or recruitment material.

Patients or their legally acceptable representatives must sign the consent form before any screening tests or assessments are performed. At the time of consent, the patient will be considered enrolled into the study and will be assigned a unique screening number before any study procedures, including screening procedures, are performed. The screening number and patient identification number must remain constant throughout the entire trial. In the event the patient is re-consented and re-screened the patient must be given a new screening number. Screening numbers and patient identification numbers, once assigned, will not be re-used.

4.2 Randomization

Patients will be randomized after all screening assessments have been completed and after the Investigator has verified that they are eligible per criteria in [Sections 5.1](#) and [5.2](#). No patient may begin treatment prior to randomization and assignment of a unique patient identification number.

Using an Interactive Web-Response System (IXRS), eligible patients will be randomized in a 1:1:1:1 ratio to 1 of the 4 parallel-dose cohorts (Cohorts A, B, C, or D). Within each dose cohort, patients will be randomized in a 4:1 ratio to receive ISIS 678354 or matching volume of placebo, respectively.

A permuted block schedule will be used. The randomization schedule will be generated and held by an independent vendor.

4.3 Replacement of Patients

Patients who withdraw from the study will not be replaced.

4.4 Unblinding of Treatment Assignment

The Sponsor and all patients, monitors, and Study Center personnel related to the study will be blinded throughout the study and until all patients have completed the study and the database has been locked. However, if a patient has suffered an SAE (as defined in [Section 9.3.3](#)), and/or when knowledge of the treatment assignment will impact the clinical management of the patient, the Investigator will have the ability to unblind the treatment assignment for that patient using the IXRS. The Sponsor will determine the point at which all treatment assignments will be unblinded. The Sponsor or designee will be informed of the unblinding of a patient within 24 hours. In addition, all SUSARs will be unblinded by the Sponsor's or designee's Drug Safety and Quality Assurance personnel for the purpose of regulatory reporting (see [Section 9.2](#)).

5. PATIENT ELIGIBILITY

To be eligible to participate in this study, candidates must meet the following eligibility criteria within 4 weeks of Study Day 1 or at the time point specified in the individual eligibility criterion listed.

5.1 Inclusion Criteria

1. Must have given written informed consent (signed and dated) and any authorizations required by local law and be able to comply with all study requirements
2. Males or females aged ≥ 18 and ≤ 80 years old at the time of informed consent
3. a. Clinical diagnosis of CVD (defined as documented coronary artery disease, stroke, or peripheral artery disease; refer to [Section 3.1](#)), OR
b. High risk for CVD defined as:
 - o Type 2 Diabetes Mellitus requiring treatment, and
 - o Age ≥ 50 years, and
 - o at least one additional CV risk factor:
 - men ≥ 55 years of age and women ≥ 65 years of age, or
 - current cigarette smoker, or stopped smoking within 3 months prior screening, or
 - hypertension requiring antihypertensive treatment
4. Fasting serum TG ≥ 200 mg/dL (≥ 2.3 mmol/L) and ≤ 500 mg/dL (≥ 5.7 mmol/L) at Screening. If the fasting TG value at Screening is < 200 mg/dL (< 2.3 mmol/L) but ≥ 150 mg/dL (≥ 1.7 mmol/L) one additional test may be performed in order to qualify
5. Fasting TG ≥ 200 mg/dL and ≤ 500 mg/dL at Qualification visit. If fasting TG is < 200 mg/dL but ≥ 150 mg/dL one additional test may be performed in order to qualify
6. Must be on standard-of-care preventative therapy for their known CVD risk factors (e.g., hyperlipidemia, hypertension, diabetes)
7. Patients on the following medications must be on a stable regimen for at least 4 weeks prior to Screening and expected to remain on a stable regimen through the end of the post-treatment follow-up period:
 - a. Lipid lowering drugs (statins, ezetimibe, PCSK9 inhibitors, niacin, fibrates, fish oil or other products containing omega-3 fatty acids including OTC preparations)
 - b. Antiplatelet drugs
 - c. Testosterone, estrogens, progesterone, growth hormone or progestins
8. Females: must be non-pregnant and non-lactating and either:
 - a. Surgically sterile (e.g., tubal occlusion, hysterectomy, bilateral salpingectomy, bilateral oophorectomy);
 - b. Post-menopausal (defined as 12 months of spontaneous amenorrhea in females > 55 years of age or, in females ≤ 55 years, 12 months of spontaneous amenorrhea without an alternative medical cause and FSH levels in the postmenopausal range for the laboratory involved);

- c. Abstinent* or,
- d. If engaged in sexual relations of child-bearing potential, agree to use 2 highly effective contraceptive methods (refer to [Section 6.3.1](#)) from the time of signing the informed consent form until at least 13 weeks after the last dose of Study Drug (ISIS 678354 or placebo)

* Abstinence is only acceptable as true abstinence, i.e., when this is in line with the preferred and usual lifestyle of the patient. Periodic abstinence (e.g., calendar, ovulation, symptothermal, post-ovulation methods), declaration of abstinence for the duration of a trial and withdrawal are not acceptable methods of contraception

- 9. Males must be surgically sterile or, if engaged in sexual relations with a female of child-bearing potential, the patient must be using an acceptable contraceptive method (refer to [Section 6.3.1](#)) from the time of signing the informed consent form until at least 13 weeks after the last dose of ISIS 678354

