6.3 Restriction on the Lifestyle of Patients

6.3.1 *Contraception Requirements*

All male patients and women of childbearing potential must refrain from sperm/egg donation and either be abstinent[†] or practice effective contraception from the time of signing the informed consent form until at least 13 weeks after their last dose of study treatment.

Male patients engaged in sexual relations with a female of child-bearing potential must also encourage their female partner to use effective contraception from the time of signing the informed consent until 13 weeks after the patient's last dose of study treatment.

For the purposes of this study, women of childbearing potential are defined as any female who has experienced menarche, and who does not meet 1 of the following conditions:

- Postmenopausal: 12 months of spontaneous amenorrhea in females > 55 years of age or, in females ≤ 55 years, 12 months of spontaneous amenorrhea without an alternative medical cause and FSH levels in the postmenopausal range for the laboratory involved
- 6 weeks after surgical bilateral oophorectomy with or without hysterectomy
- Post hysterectomy

For the purposes of the study, effective contraception is defined as follows:

For male patients:

- Effective male contraception includes a vasectomy with negative semen analysis at Follow-up, or the use of condoms together with spermicidal foam/gel/film/cream/suppository
- Male patients with partners that are pregnant must use condoms as contraception to ensure that the fetus is not exposed to the Study Drug

For female patients and female partners of male patients:

- Using 2 of the following acceptable methods of contraception: surgical sterilization (e.g., bilateral tubal ligation), hormonal contraception, intrauterine contraception/device, or any 2 barrier methods (a combination of male or female condom* with diaphragm, sponge, or cervical cap) together with spermicidal foam/gel/film/cream/suppository

†Note: Abstinence is only acceptable as true abstinence, i.e., when this is in line with the preferred and usual lifestyle of the patient. Periodic abstinence (e.g., calendar, ovulation, symptothermal, post-ovulation methods), declaration of abstinence for the duration of a trial and withdrawal are not acceptable methods of contraception.

***Note:** A female condom and a male condom should not be used together as friction between the 2 can result in either or both products failing.

6.3.2 *Other Requirements*

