Any event meeting renal stopping rules criteria described in [Section 8.6.2](#) is considered an adverse event of special interest and should be reported in an expedited fashion to the Sponsor as per [Sections 9.3.3.1](#) and [9.4.1](#)).

9.5.2 *Prescheduled or Elective Procedures or Routinely Scheduled Treatments*

A prescheduled or elective procedure or a routinely scheduled treatment will not be considered an SAE, even if the patient is hospitalized; the Study Center must document all of the following:

- The prescheduled or elective procedure or routinely scheduled treatment was scheduled (or was on a waiting list to be scheduled) prior to obtaining the patient's consent to participate in the study
- The condition that required the prescheduled or elective procedure or routinely scheduled treatment was present before and did not worsen or progress in the opinion of the Investigator between the patient's consent to participate in the study and the timing of the procedure or treatment. The condition is documented in the patient's medical history
- The prescheduled or elective procedure or routinely scheduled treatment is the sole reason for the intervention or hospital admission

9.5.3 *Dosing Errors*

Study Drug (ISIS 678354 or placebo) errors should be documented as Protocol Deviations. A brief description should be provided in the deviation, including whether the patient was symptomatic (list symptoms) or asymptomatic, and the event was accidental or intentional.

Dosing details should be captured on the Dosing Case Report Form. If the patient takes a dose of Study Drug (ISIS 678354 or placebo) that exceeds protocol specifications and the patient is symptomatic, then the symptom(s) should be documented as an AE and be reported per [Section 9.4](#).

Should an overdose occur, the Investigator or designee should contact the Sponsor or designee within 24 hours.

9.5.4 *Contraception and Pregnancy*

Male and female patients of childbearing potential must continue to use appropriate contraception with their partners, or refrain from sexual activity, as described in [Section 6.3.1](#).

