Appendix A Schedule of Procedures – Weekly and Every 2-Week Dosing *Continued*

All procedures and study samples are to be done pre-dose at respective visits, unless specified

- a Visit only required for patients in PK subgroup.
- b Day 1/Baseline assessments can be performed up to 3 days (-3 days) prior to the actual Day 1 visit, which is the day of first Study Drug dose.
- c Patient charts will be reviewed in order to collect disease associated medical history data such as CVD history.
- d Height only required at Screening.
- e All tests listed in [Appendix B](#) under Extended Urinalysis should be performed, including routine urinalysis, urine microscopy, UACR and UPCR.
- f Assessments and procedures to be conducted by either a home healthcare service or the Study Center. Patient Study Center visits must be no more than 4 weeks apart during the treatment period.
- g Urine samples for renal biomarkers will be collected. Sample analysis will be conducted in accordance with Safety Monitoring for Renal Function.
- h During follow-up period, hematology sampling for platelet values are taken every 14 days for 6 weeks after treatment period, then at the Week 8 and Week 13 Follow-up visits.
- i Serum Creatinine and Cys-C will be collected as a part of chemistry panel at visits when chemistry panel is performed, or as stand-alone samples at time points when a chemistry panel is not performed.
- j Blood samples to be collected after an overnight fast of at least 10 hours and preferably not more than 12 hours, unless tests are repeated for safety reasons.
- k If the platelet value, serum creatinine or liver enzyme tests are uninterpretable (e.g., due to clumping, hemolysis or quantity not sufficient) a repeat blood specimen should be re-drawn as soon as possible (ideally within 7 days). All platelet count results will be reviewed promptly (within 48 hours of receipt) by the Investigator. Any case of a platelet count < 50,000/mm³ should be reported in an expedited fashion to the Sponsor.
- l Refer to [Appendix C](#) for PK Sampling schedule.
- m Women who are not surgically sterile or post-menopausal.
- n Serum and plasma samples will be collected and stored for follow-up exploration of laboratory findings and/or AEs (e.g., measurement of cytokine and/or chemokine levels, measurement of additional markers of kidney function, measurement of antibodies, etc.) and will be retained until completion of the final study report.

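### Criterion 8a treats tubal procedures as surgical sterility, Section 6.3.1 does not, and the footnote that limits scheduled pregnancy tests can be read either way

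*Combined protocol and SAP*

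**What the plan says.** Criterion 8 (Section 5.1, repeated in the synopsis) says that females "must be non-pregnant and non-lactating" and must also meet one of four alternatives.

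- **8a** is surgical sterility: "Surgically sterile (e.g., tubal occlusion, hysterectomy, bilateral salpingectomy, bilateral oophorectomy". It suffices alone and carries no contraception duty.
- **8d** carries that duty. Women taking this route "agree to use 2 highly effective contraceptive methods", with a reference to Section 6.3.1.

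Section 6.3.1 uses a different concept. For the study, "women of childbearing potential are defined as any female who has experienced menarche, and who does not meet 1 of the following conditions". The three conditions are post-menopausal status, six weeks elapsed since bilateral oophorectomy, and previous hysterectomy. Among contraceptive options the section gives: "Using 2 of the following acceptable methods of contraception: surgical sterilization (e.g., bilateral tubal ligation". Tubal ligation is thus one method of the two required.

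Section 9.5.4 applies the contraception rule during the study: "Male and female patients of childbearing potential must continue to use appropriate contraception with their partners, or refrain from sexual activity".

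In both Appendix A schedules the Serum Pregnancy Test row carries footnote m, which reads: "Women who are not surgically sterile or post-menopausal". The FSH row shares it.

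**The concern.** A pre-menopausal woman whose only procedure was tubal occlusion or bilateral salpingectomy is surgically sterile in the eligibility criteria and of childbearing potential in the section that governs conduct on study. Footnote m borrows the first term, not the second, and does not define it. A site that follows each section literally could require contraception of her and still skip her scheduled pregnancy tests.

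The protocol treats the matter as important. Contraception runs to at least 13 weeks after the last dose, pregnancy requires permanent discontinuation of Study Drug (Section 8.8), and Section 2.3.4 describes a long terminal half-life, so stopping the drug does not end exposure at once. What is at stake is later detection of a pregnancy in a small group of women. Sample size, Type I error and the efficacy estimates are unaffected.

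**Working it through.** The plan gives no figure to reproduce, so the check compares the texts and then counts tests.

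**Step 1. Compare the definitions by procedure, for a pre-menopausal woman.**

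| Procedure | Criterion 8a | Section 6.3.1 | Agree? |
|---|---|---|---|
| Hysterectomy | sterile | not of childbearing potential | yes |
| Bilateral oophorectomy | sterile | not of childbearing potential from 6 weeks after surgery | yes, apart from the wait |
| Tubal occlusion | sterile | of childbearing potential; ligation is one of two methods | no |
| Bilateral salpingectomy | sterile | of childbearing potential; not named as an exemption or as a method | no |

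Post-menopausal status is defined the same way in 8b and Section 6.3.1, so that part of footnote m causes no conflict.

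**Step 2. Apply footnote m to the two conflicting rows.** Read with 8a, whose term it shares, the footnote exempts both women from scheduled tests. Read with the Section 6.3.1 definition, it exempts neither. For tubal ligation the exempting reading gains some support because Section 6.3.1 itself calls it surgical sterilization. Section 6.3.1 contains no testing rule that would settle the matter.

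**Step 3. Count the tests that could be skipped.** Inputs are the marks in the Serum Pregnancy Test row of each Appendix A schedule, as extracted.

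- Weekly and every-2-week schedule: 3 (Screening, Qualification, Day 1) + 5 (Weeks 5 to 21) + 10 later marks = 18.
- Every-4-week schedule: 3 + 5 + 9 later marks = 17.
- Six-month course, with the Week 53/ET procedures done at End of Treatment (Section 3.4.2; footnote q lets Week 27 or Week 25 serve as that visit): 3 + 5 + 1 + 3 follow-up = about 12.
- With the Appendix B screening hCG done, each count falls by one: 17, 16 and about 11.

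The full-course figures are not upper bounds. Each header shows 11 standard visits from the primary time point onward (eight from Week 27 or Week 25 to Week 53/ET, and three in follow-up), but only 10 and 9 marks were extracted. If every one of those visits were marked, the total would be 3 + 5 + 11 = 19. The difference between 18 and 17 may itself come from extraction.

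**Step 4. Number of women.** The documents give no count. Assume that 0%, 1%, 3% or 5% of about 100 patients (Section 3.3) are affected: 100 × share = 0, 1, 3 or 5 women. With 4:1 allocation, × 0.8 = 0, 0.8, 2.4 or 4 on active drug. The high-risk route (criterion 3b) requires age 50 or over, so younger women enter only with documented CVD.

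**The case against.** The strongest reply is that nothing strictly contradicts. Criterion 8a is an entry route with open-ended examples. Section 6.3.1 defines childbearing potential, not sterility. A woman can enter under 8a and then follow Section 6.3.1. For contraception this stands: with Section 9.5.4 it largely settles what she must do. A reader might infer that the protocol leaves her without a contraception rule, and the documents do not support that.

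The reply does not settle testing. A reader might equally infer that the protocol excludes her from pregnancy tests. That also goes too far: footnote m leaves its term undefined, and a site could apply Section 6.3.1 and test her. The text supports only that the footnote can be read to omit her tests.

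The safeguards are also real. Every female must be non-pregnant at entry. Appendix B lists a screening hCG for women with no sterility limit. During treatment, "Patient Study Center visits must be no more than 4 weeks apart during the treatment period". Section 9.5.4 requires a test when pregnancy is suspected. These reduce the consequence, but a test on suspicion does not replace a scheduled one.

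Finally, the sections could be made to agree in the other direction, by exempting tubal procedures in Section 6.3.1. For tubal ligation that would reverse what Section 6.3.1 already decides by counting it as one method of two. For bilateral salpingectomy the objection holds: Section 6.3.1 does not name it, and either classification would be consistent.

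**Conclusion.** The definitions differ, and this can be stated with high confidence. The consequence is narrower: an ambiguous footnote that may remove scheduled pregnancy tests for a pre-menopausal woman with only a tubal procedure. The size is roughly 17 to 18 scheduled tests per affected woman over a full course and about 12 over six months, subject to the damaged table rows and fewer after early discontinuation. The number of women rests wholly on the assumed 0% to 5%; it is likely small and may be zero. This is a minor safety-wording point, worth correcting because correction is cheap.

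**What to change.** Use one definition throughout.

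1. In both Appendix A schedules, key the Serum Pregnancy Test row to women of childbearing potential as defined in Section 6.3.1. Give the FSH row its own footnote, for women aged 55 or younger whose post-menopausal status has to be established. FSH feeds the definition and should not depend on it.
2. In criterion 8a, in Section 5.1 and the synopsis, refer to Section 6.3.1 instead of listing separate examples.
3. State that tubal occlusion or ligation counts as one of the two methods, so that one further listed method or true abstinence is needed. Criterion 8d should say that its two methods are those listed in Section 6.3.1, which labels them acceptable and calls none highly effective.
4. Decide bilateral salpingectomy explicitly. Either add it to the Section 6.3.1 exemptions, with no further method and no scheduled tests, or remove it from 8a and say in Section 6.3.1 that it counts as one method.

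The cost is a few wording changes. Each woman newly covered has about 11 serum tests after Screening on a six-month course, or about 16 to 17 on a full course as extracted, mostly at visits where blood is already drawn. If no such woman enrolls, there is no patient burden.
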